16.0 Safety Assessments and Monitoring

16.1 Definition of an Adverse Event

An AE is any untoward medical occurrence associated with the use of a drug in humans, whether or not considered drug related. An AE can therefore be any unfavorable and unintended sign (including an abnormal laboratory finding), symptom or disease temporally associated with the use of a study drug/study intervention, whether or not related to the study drug/study intervention.

Any laboratory abnormality that is deemed to be clinically significant in the opinion of the investigator will be considered an AE and should be recorded in the eCRF, whether or not it is related to the study drug.

Stable chronic conditions that are present prior to clinical trial enrollment and do not worsen are not considered AEs and will be accounted for in the subject's medical history.

The following can be considered AEs:

- An exacerbation of a pre-existing illness
- An increase in frequency or intensity of a pre-existing episodic event or condition
- A condition detected or diagnosed after the initiation of treatment with study medication, even though it may have been present prior to the start of the study
- Continuous persistent disease or symptoms present at Baseline that worsen after signing the informed consent or following the initiation of treatment with study medication

The following are **not** considered AEs:

- Medical or surgical procedures (e.g., surgery, endoscopy, tooth extraction or transfusion); the condition that leads to the procedure is an AE
- Pre-existing disease or conditions present or detected at the start of the study that do not worsen
- Situations where an untoward medical occurrence has not occurred (e.g., hospitalizations for cosmetic surgery or elective surgery or social/convenience admissions)

- The disease being studied or signs or symptoms associated with the disease, unless more severe than expected for the subject's condition or a worsening of the disease being studied

16.2 Definition of a Serious Adverse Event

A SAE is defined as an AE meeting one of the following outcomes:

- Death
- Life-threatening event
- Inpatient hospitalization or prolongation of existing hospitalization
- Persistent or significant disability/incapacity or substantial disruption of the ability to conduct normal life functions
- Congenital anomaly or birth defect

Any other important medical event that may not result in one of the above outcomes may be considered a SAE when, based upon appropriate medical judgment, the event may jeopardize the participant and may require medical or surgical intervention to prevent one of the outcomes listed above.

A life-threatening AE is any AE that places the subject, in the view of the investigator, at immediate risk of death from the AE as it occurred. It does not include an AE that, had it occurred in a more severe form, might have caused death.

16.3 Events of Clinical Interest

The following are considered events of clinical interest (ECIs) if they occur after dosing, and must be reported by the site when it becomes aware of the ECI:

- ALT or AST > 8 x the upper limit of normal (ULN), confirmed by repeat testing
- ALT or AST > 5 x ULN for more than 2 weeks if new compared to Baseline, confirmed by repeat testing
- ALT or AST > 3 x ULN **and** total bilirubin >2 x ULN if new compared to Baseline, confirmed by repeat testing
- ALT or AST > 3 x ULN, confirmed by repeat test, with the appearance of fatigue, nausea, vomiting, right upper quadrant pain or tenderness, fever, rash, and/or eosinophilia (> 5%)

16.4 Overdose

This refers to the administration of a quantity of a medicinal product given per administration or cumulatively, which is above the maximum recommended dose according to the authorized product information. Considering the dosing schedule in this study, one dose administered at the site and one dose administered at home approximately 12 hours later, overdose is not expected. If accidentally the 2 doses of study drug are administered together, this should be recorded in the dosing section of the eCRF but will not require additional reporting unless associated with a SAE. An overdose must be reported within 24 hours of the site becoming aware of the overdose if such overdose occurs with an associated SAE.

16.5 Pregnancy

Female subjects who become pregnant should be immediately discontinued from the study and followed up to determine the outcome of the pregnancy. The pregnancy must be reported to the Sponsor within 24 hours of the site becoming aware of the pregnancy. If the pregnancy ends for any reason before the anticipated date, the investigator should notify the Sponsor. At the completion of the pregnancy, the investigator will document the outcome of the pregnancy. If the outcome of the pregnancy meets the criteria for immediate classification as an SAE (i.e., postpartum complication, spontaneous abortion, stillbirth, neonatal death or congenital anomaly), the investigator should follow the procedures for reporting an SAE.

16.6 Unexpected Adverse Event

An AE is considered “unexpected” if it is not listed in the IB or is of greater specificity or severity than those that have been observed with the particular study drug being tested. For example, under this definition, hepatic necrosis would be unexpected (by virtue of greater severity) if the IB referred only to elevated hepatic enzymes or hepatitis. Similarly, cerebral thromboembolism and cerebral vasculitis would be unexpected (by virtue of greater specificity) if the IB listed only cerebral vascular accidents. "Unexpected," as used in this definition, also refers to AEs that are mentioned in the IB as occurring with a class of drugs or as anticipated from the pharmacological properties of the drug but are not specifically mentioned as occurring with the particular drug under investigation.

16.7 Grading of Adverse Events

The severity (or intensity) of an AE refers to the extent to which it affects the subject's daily activities and will be classified by the investigator as mild, moderate or severe using the following criteria:

- Mild: Awareness of sign or symptom, but easily tolerated. Not likely to require medical attention.
- Moderate: Discomfort enough to cause some interference with daily activity. May require medical intervention.
- Severe: Intense enough to disrupt daily activities. Likely requires medical intervention.

Clarification of the difference in meaning between “severe” and “serious”

The term “severe” is often used to describe the intensity (severity) of a specific event (as in mild, moderate or severe myocardial infarction); the event itself, however, may be of relatively minor medical significance (such as severe headache). This is not the same as “serious”, which is based on the outcome or action criteria usually associated with events that pose a threat to life or functioning. Seriousness (not severity) serves as a guide for defining regulatory reporting obligations.

16.8 Causality Assessment

The investigator will assess causality (i.e., whether there is a reasonable possibility that the study drug caused the event) for all AEs and SAEs. The relationship will be characterized using the following classification:

- Related: The temporal relationship of the AE with the study drug makes causality possible and as likely or more likely than due to another cause such as other drugs, a surgical intervention or an underlying disease.
- Not related: The temporal relationship of the AE with the study drug makes causality improbable and can be due to another cause such as other drugs, a surgical intervention or an underlying disease.

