16.10 Serious Adverse Event Reporting Requirements

All SAEs must be reported within 24 hours of the site becoming aware of the SAE. Any event that is serious, study drug-related, and unexpected as assessed by the medical monitor or the Sponsor will be submitted to the regulatory authorities in accordance with national regulatory laws and regulations. The PI will be responsible for reporting all SAEs that require reporting to the local or central Institutional Review Board/Ethics Committee (IRB/EC) in accordance with its regulations and guidelines.

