9.1.1. Treatment-Emergent Adverse Events

Summaries of the total number of TEAEs and the number and percentage of subjects with at least one TEAE will be provided by treatment. Treatment-emergent AEs will be presented by SOC and PT. At each level of subject summarization, a subject is counted once if the subject reported one or more events. Percentages will be calculated out of the number of subjects in the safety set.

The summary of TEAEs will be presented in alphabetical order of SOC. Within each SOC, PTs will be sorted in descending order from the PT with the highest total frequency (that is, summed across all treatment groups) to the PT with the lowest total frequency. If the total frequency for any two or more PTs is equal, the PTs will be presented in alphabetical order.

The summarization described above will also be repeated for the following:

- Serious Adverse Events;
- Treatment-Related Adverse Events;
- Treatment-Related Serious Adverse Events;
- Adverse Events Leading to Dose Interruption.

The adverse events with a missing relationship will be considered as “Treatment Related” in the tables.

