9.1.2. Relationship of Adverse Events to Study Treatment

A summary of TEAEs by relationship to study treatment will be presented in a table. The investigator will provide an assessment of the relationship of the event to the study treatment. The possible relationships are “Not Related” and “Related”. In the TEAE relationship table, if a subject reports multiple occurrences of the same TEAE, only the most closely related occurrence will be presented. Treatment-emergent AEs that are missing a relationship will be presented in the summary table as “Related” but will be presented in the data listing with a missing relationship. Percentages will be calculated based on the number of subjects in the safety set.

The TEAE data will be categorized and presented by SOC, PT, and relationship in a manner similar to that described in Section 9.1.1.

Treatment-emergent SAEs by relationship to study treatment will also be presented in a table. Treatment-emergent SAEs that are missing a relationship will be presented in the table as “Related” but will be presented in the data listing with a missing relationship.

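### Protocol 16.8 asks about a reasonable possibility of drug causation, but its two causality categories do not match that test and leave a gap, so treatment-related AEs may be under-counted or coded differently between sites

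*Protocol*

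**What the plan says.** Protocol 16.8 (Causality Assessment) has the investigator assess every AE and SAE for "whether there is a reasonable possibility that the study drug caused the event". It then gives two categories.

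- **Related:** "The temporal relationship of the AE with the study drug makes causality possible and as likely or more likely than due to another cause". The examples of other causes are other drugs, surgery and underlying disease.
- **Not related:** "The temporal relationship of the AE with the study drug makes causality improbable and can be due to another cause", with the same examples.

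SAP 9.1.2 keeps these two levels and has no intermediate one such as possibly related. It plans the main output as follows: "A summary of TEAEs by relationship to study treatment will be presented in a table". For blanks, SAP 9.1.1 states: "The adverse events with a missing relationship will be considered as “Treatment Related” in the tables". SAP 9.1.2 repeats that rule for the relationship tables.

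Protocol 16.10 makes relatedness one of three conditions for submission to regulators: "Any event that is serious, study drug-related, and unexpected as assessed by the medical monitor or the Sponsor".

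**The concern.** A compulsory two-way classification should cover every case and should agree with the question it answers. This one does neither. Take an AE that follows dosing closely enough for the drug to be a real candidate, in a subject with another, likelier explanation such as a concomitant medicine. The answer to the opening question is yes. The Related definition excludes the event because the drug is the less likely cause. The Not related definition excludes it because drug causation is not improbable.

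The investigator's choice feeds several outputs: the overview counts of treatment-related and treatment-related serious TEAEs (SAP 9.1), the treatment-related AE and SAE tables (9.1.1), the relationship tables (9.1.2) and the table by severity and relationship (9.1.3). With about 30 centres (Protocol 10.4), the same kind of event could be coded in different ways. The SAP's conservative rule does not help, because it acts on a missing relationship and an event entered as Not related is not missing.

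**Working it through.** There is no plan figure to reproduce. The check is a logical one on the definitions.

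**Notation.** For one AE, let *p* be the investigator's judged likelihood that the drug caused it and *q* the likelihood of another cause.

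**Conditions, all from Protocol 16.8.**
- Opening test: *p* is a reasonable possibility.
- Related: causality is possible and *p* ≥ *q*.
- Not related: causality is improbable and another cause can explain the event.

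**Cases.**

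| Event | Opening test | Related | Not related |
|---|---|---|---|
| Reasonable possibility, *p* ≥ *q* | met | met | not met |
| Reasonable possibility, *p* < *q* | met | not met | not met |
| Improbable, another cause explains it | not met | not met | met |

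Two results follow from the second row.

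1. The categories are not exhaustive.
2. Related is stricter than the opening test, because a reasonable possibility does not require the drug to be the equal or leading explanation.

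**Size.** Among AEs that pass the opening test, let *g* be the share in the second row, and *s* the share of those that sites record as Not related. Then

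share of such AEs lost from the related count = *g* × *s*.

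- If sites follow the opening test, or leave the field blank so that the SAP counts the event as related, *s* = 0 and the loss is 0.
- If every such event is recorded as Not related, *s* = 1 and the loss is *g*.

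The documents give neither *g* nor *s*, so the range is 0 to *g* with *g* unknown. This share is per event. SAP 9.1.2 presents only the most closely related occurrence when a subject reports the same TEAE more than once, so the loss in subject counts can be smaller.

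**Reach.**

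| Output | Depends on the 16.8 category? |
|---|---|
| Treatment-related TEAE and SAE tables (SAP 9.1 to 9.1.3) | yes |
| All TEAEs by arm, SOC and PT (SAP 9.1.1) | no |
| TEAEs by severity alone (SAP 9.1.3) | no |
| Site reporting of SAEs (Protocol 16.12) | no, required whether or not judged related |
| Hepatic events of clinical interest (Protocol 16.3, SAP 9.2.2) | no, laboratory and clinical criteria |
| Efficacy analyses (SAP 8) | no |
| Submission to regulators (Protocol 16.10) | relatedness is a condition; assessment lies with the medical monitor or sponsor |

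**The case against.** A reader might infer that drug-related AEs *are* under-counted. The documents do not support that. A gap event fails the Not related definition as well, since that one "makes causality improbable and can be due to another cause", so the text pushes it into neither category. An investigator who resolves the doubt by the opening question records Related, and a blank is counted as related. One can argue that the comparative clause is the working definition of Related, so that an event failing it drifts to the only other box. That is a plausible tendency, not something the documents show.

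A reader might also try to size the loss from the Phase 2b gastrointestinal rates for this dose in Protocol 7.1 (diarrhoea or loose stool in five patients, 17%; nausea in three, 10%). Those are all-cause rates from a handful of patients. They count patients, so they cannot be added as events, and they say nothing about how often causality was in doubt. Gastrointestinal events are also the drug's most frequently reported AEs, so an investigator could readily judge the drug at least as likely as another cause.

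The safeguards are real. In a randomised, double-blind, placebo-controlled trial the all-TEAE comparison by arm measures drug effect without any attribution. All SAEs reach the sponsor regardless of relationship. Protocol 16.10 gives the assessment for submission to the medical monitor or sponsor and does not tie it to the 16.8 category wording. The wording applies equally to both arms, so it does not by itself favour one, although it can blur a difference in related AEs.

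What remains is the inconsistency within 16.8 itself, which none of these points removes.

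**Conclusion.** The point holds as a minor inconsistency in a stated rule. The opening test and the two definitions in 16.8 disagree, and one realistic kind of AE has no valid category. Treatment-related TEAEs and SAEs may therefore be under-counted or classified inconsistently between sites. The size cannot be derived from the documents and may be zero. It depends on how many AEs have a reasonable but less likely drug cause and on how sites code them. The effect is confined to the investigator's causality entry and the relationship-based safety tables.

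**What to change.** In Protocol 16.8, replace the two definitions with a pair that covers every case and uses the opening test:

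- *Related: drug causation is a reasonable possibility.*
- *Not related: drug causation is not a reasonable possibility.*

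Delete the clause comparing the drug's likelihood with that of another cause. Keep timing and alternative causes (other drugs, surgery, underlying disease) as factors the investigator should weigh, because a bare restatement of the test would remove guidance that helps sites agree. Carry the same wording into the eCRF completion guide. The SAP tables and the rule for a missing relationship can stay as they are.

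The change costs two sentences and an update to the guide. The downside is a somewhat higher count of related events in both arms. If AEs have already been coded under the present wording, those entries should be queried while the study is still blinded, or the tables will mix two definitions.

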16.9 Adverse Event Collection Timeframe

All AEs and SAEs will be recorded from the time informed consent is obtained through the FU visit (end of study).

All AEs reported by the subject or observed by members of the clinical staff will be evaluated by the principal investigator (PI) or qualified designee. The PI will attempt, if possible, to establish a diagnosis based on presenting signs and symptoms. The nature of the AE, time of onset relative to study drug administration, duration, severity, and relationship to treatment should be determined. Details of any corrective treatment must be recorded in the eCRF. The PI will determine whether any changes have occurred in baseline signs and symptoms. All AEs and SAEs will be collected in the eCRF.

16.10 Serious Adverse Event Reporting Requirements

All SAEs must be reported within 24 hours of the site becoming aware of the SAE. Any event that is serious, study drug-related, and unexpected as assessed by the medical monitor or the Sponsor will be submitted to the regulatory authorities in accordance with national regulatory laws and regulations. The PI will be responsible for reporting all SAEs that require reporting to the local or central Institutional Review Board/Ethics Committee (IRB/EC) in accordance with its regulations and guidelines.

16.11 Adverse Event and Serious Adverse Event Follow-up

All AEs and SAEs will be followed up to resolution (the subject's health has returned to her baseline status or all variables have returned to normal) or until an outcome is reached, stabilization occurs (the investigator does not expect any further improvement or worsening of the event) or the event is otherwise explained, regardless of whether the subject is still participating in the study. All appropriate therapeutic measures should be undertaken and recorded. Where appropriate, medical tests and examinations will be performed to document resolution of the event(s).

16.12 Serious Adverse Event Reporting – Procedures for Investigators

Initial Reports and Follow-Up SAE Reports: To report an SAE, the SAE eCRF form within the Electronic Data Capture (EDC) system must be completed. All SAEs, whether or not deemed drug-related or expected, must be reported by the investigator or qualified designee within 24 hours of first becoming aware of the event. The investigator/qualified designee will enter the required information regarding the SAE into the appropriate form, which will automatically result in distribution of the information to the appropriate sponsor contact

If the EDC system is temporarily unavailable (>24 hours), the event, including the investigator-determined causality to study drug, should be reported via a paper back-up SAE form to the Safety Surveillance team via (contact information, i.e., e-mail or fax will be available on the SAE form).

Upon return of the availability of EDC system, the SAE information must be entered into the EDC system as soon as possible. The SAE form within the EDC system must be updated within 24 hours of knowledge/receipt of SAE follow-up information.

16.13 Procedures for Emergency Unblinding

This is a double-blind, double-dummy study. The Investigator should only be unblinded if it is necessary to determine treatment of emergency. The study personnel responsible for the treatment assignment can provide the information necessary to unblind the investigator (evaluator), in case of an emergency. If the evaluator is unblinded, the reason for unblinding should be documented in the comment page of the eCRF.

17.0 Data Collection, Study Monitoring and Record Management

17.1 Data Collection and Reporting

Data for this study will be collected using eCRFs. The investigator and study site staff will receive training regarding the completion of the eCRF. Visit-specific data should be entered into the eCRF and be ready for review as soon as possible, but no later than 5 days after each visit/time point.

All protocol-required information collected during the study must be entered by the investigator or designated representative in the source documents and eCRF. All data entry, modification or deletion will be recorded indicating the individual subject, original value, the new value, the reason for change, who made the change, and when the change was made. All data changes will be clearly indicated with a means to locate prior values. The investigator will maintain a list of individuals who are authorized to enter or correct data on the eCRFs.

The investigator or designated sub-investigator, following review of the data in the eCRF, will confirm the validity of each subject's data by signing the eCRF.

17.2 Study Monitoring

Study progress will be monitored by the Sponsor or its representative as frequently as necessary to ensure adequate and accurate data collection, protocol compliance, and study conduct in accordance with accepted regulatory requirements. The PI must make all the

subject data available to the monitor for review during the planned site monitoring visits. Arrangements for monitoring visits will be made in advance, except in emergency cases.

17.3 Investigator Study Files

The PI is responsible for maintaining all study-related documents in study files. The Sponsor will notify the PI when retention of study files is no longer necessary. The following documents will be kept in the study files or be readily accessible:

- original protocol and all amendments;
- signed agreement or protocol;
- signed and dated study staff roles and responsibilities log;
- copy of the current *curriculum vitae* of the PI and of all sub-investigators;
- IRB/EC membership list and all IRB/EC approvals for the protocol and amendments, informed consent documentation and all updates, advertisements, and written information provided to subjects; all IRB/EC correspondence; documentation that the IB and subsequent revisions have been submitted to the IRB/EC; documentation that all SAEs and any periodic safety reports have been submitted to the IRB/EC; and annual IRB/EC renewals (as required);
- updated laboratory certification and the laboratory's normal values (covering the entire time interval of the study for all laboratory tests conducted during the study);
- all confirmations of investigational drug receipt, drug accountability logs and drug return records;
- a CD or DVD containing final subject eCRF data;
- all correspondence to or from the Sponsor or its designees;
- blank informed consent form;
- Investigator's Brochure;
- subject screening log;
- subject list (contains subject initials and/or protocol-specific subject number);
- all subjects' original signed informed consents; and,
- monitoring visit log.

